CLINICAL STUDY PROTOCOL

Screening for Cardiac Amyloidosis with Nuclear imaging in Minority Populations study (SCAN-MP)

Protocol Version:

4.2

Protocol Date:

June 24, 2022

ClinicalTrials.gov:

NCT03812172

Sponsor:

Columbia University Medical Center
Clinical Cardiovascular Research Laboratory for the
Elderly (CCRLE)
[name]
[name]

Sponsor-Investigator:

[name]
Co-Principal Investigator
[contact]

[name]
Co-Principal Investigator
[contact]

Site Investigator:

[name]
Site Investigator
[contact]

Collaborating Investigators: [name]
Abbott Diagnostics

[name]
Abbott Diagnostics

STUDY SYNOPSIS

Protocol Title	Screening for Cardiac Amyloidosis with Nuclear imaging in Minority Populations study (SCAN-MP)
Protocol Number	4.2
Design	
This is a multicenter, diagnostic screening study to evaluate the prevalence of wild-type and Val122Ile ATTR cardiac amyloidosis (ATTR-CA) in a population of Black and Hispanic subjects with heart failure at participating sites. ATTR-CA is an age-related infiltrative cardiomyopathy that causes heart failure and death that is frequently unrecognized and underdiagnosed.
 
Consented eligible patients will be evaluated for the presence and clinical manifestations of ATTR Cardiac Amyloidosis.
 
Patients will undergo a Screening/Baseline visit, using nuclear medicine screening and TTR genetic test. Those who have myocardial retention of the imaging radiotracer with a Perigini score ≥ 2 (uptake equal to bone) and/or H/CL ratio > 1.3 will be diagnosed with ATTR amyloidosis and followed up in 6 months and again at 12 months.

Study Sites	This study is to be conducted at five study sites: Recruitment and Screening at Harlem Hospital. All study procedures at NYP Allen Hospital, NYP Milstein Hospital, Boston University Medical Center and Yale New Haven Hospital.
Time on Study	The duration of patient participation in this study is approximately 12 months.
Primary Objective	To improve identification of minority patients with ATTR-CA and enhance the understanding of genotype-phenotype associations in Blacks/Hispanics with ATTR-CA due to the Val122Ile mutation or ATTR wild-type.
Sample Size	Up to 800 patients will be screened in this study.
Inclusion and Exclusion Criteria	
Every participant must meet all of the following inclusion criteria to be eligible for enrollment in this study:
 
 1. Black or Hispanic of Caribbean origin. 2. Age ≥ 60 years. 3. Diagnosis of heart failure, confirmed by one of two methods: 
 a. Modified criteria utilized by Rich et al. which include a history of acute pulmonary edema or the occurrence of at least two of the following that improved with diuretic therapy without another identifiable cause: dyspnea on exertion, paroxysmal nocturnal dyspnea, orthopnea, bilateral lower extremity edema or exertional fatigue, and

	
b. NHANES CHF criteria with a score ≥ 3 (see Appendix 1).
 
 4. Left ventricular septal OR inferolateral wall thickness ≥ 12 mm. 5. Ejection fraction $> 30\%$. 6. Able to understand and sign the informed consent document after the nature of the study has been fully explained. 
The presence of any of the following excludes eligibility for enrollment in this study:
 
 1. Primary amyloidosis (AL) or secondary amyloidosis (AA). 2. Prior liver or heart transplantation. 3. Active malignancy or non-amyloid disease with expected survival of less than 1 year. 4. Heart failure, in the opinion of the investigator, primarily caused by severe left-sided valve disease. Note: if valve was repaired, subject may be considered as no longer with severe valve disease. 5. Heart failure, in the opinion of the investigator, primarily caused by ischemic heart disease. 6. Ventricular assist device or anticipated within the next 6 months. 7. Impairment from stroke, injury or other medical disorder that precludes participation in the study. 8. Disabling dementia or other mental or behavioral disease. 9. Enrollment in a clinical trial not approved for co-enrollment. 10. Expected use of continuous intravenous inotropic therapy in the next 6 months. 11. High risk for non-adherence as determined by screening evaluation. 12. Inability or unwillingness to comply with the study requirements. 13. Chronic kidney disease with eGFR < 15 mL/min/1.73 m² or ESRD. 14. Weight > 350 lb. 15. Nursing home resident. 16. Other reason that would make the subject inappropriate for entry into this study.
Aims	
The specific aims of this epidemiologic investigation include:
 
 1. To determine the prevalence of ATTR Val122Ile CA in Caribbean Hispanics and Blacks with HF. 2. To demonstrate that circulating RBP4 concentration is integral to TTR tetramer stability which in turn determines the clinical

	
characteristics of ATTR CA.
 
We will explore the following:
 
 1. The prevalence of the Val122Ile genotype and ATTRm CA phenotype among Hispanics of Caribbean origin compared to Blacks. 2. Gender differences in ATTR-CA identified by myocardial uptake of Tc99-PYP or Tc99-HMDP. 3. The development of a risk based calculator based on clinical, electrocardiographic, echo and biochemical variables to identify ATTR-CA. 4. Disease progression and prognosis between Val122Ile vs. ATTRwt in this population so as to inform whether the genetic form of this condition results in a more malignant phenotype. 5. Differences in ATTR stability between ATTRm Val122Ile vs ATTRwt and non-amyloid controls which will associate with clinical features and outcomes. 6. Differences in RBP4 concentrations in plasma and urine in ATTRm Val122Ile vs ATTRwt and non-amyloid controls and their association with genetic penetrance in ATTRm V122I and prognosis.
Safety Assessments	
The safety of study participants will be evaluated by:
 
 1. Assessment of adverse events (AEs), including serious adverse events (SAEs). 2. Clinical laboratory safety tests (serum chemistry). 3. Vital sign measurements (blood pressure, pulse rate, and respiratory rate). 4. 12-Lead electrocardiogram (ECG). 5. Physical examinations

SCHEDULE OF ACTIVITIES The following table summarizes the activities to be performed at each of the designated study visits. Details of the different procedures can be found in subsequent sections of this manual.

Procedure	Screening	Baseline	6 Months* (±2 Weeks)	12 Months* (±4 Weeks)
Informed Consent	X			
Inclusion and Exclusion Criteria	X			
Baseline History		X		
Height and Weight [†]		X	X	X
Vitals Signs		X	X	X
Medications		X	X	X
Clinical Examination		X	X	X
Adverse Events Review		X	X	X
Electrocardiogram		X	X	X
Laboratory Analysis				
Basic Metabolic Panel		X	X	X
Hepatic Function Panel		X	X	X
Cardiac Biomarkers [‡]		X	X	X
Vitamin A/RBP4 in plasma/urine [§]		X	X	X
Prealbumin		X	X	X
TTR Kinetic Stability		X		X
TTR Gene Sequencing		X		
Ancestry Analysis		X		
Six-Minute Walk Test		X	X	X
Short Physical Performance Battery		X	X	X
QoL Questionnaires		X	X	X
Health Literacy Questionnaire		X		
Echocardiogram		X		X
^{99m} Tc-PYP Scintigraphy**		X		
Phone Call Follow-Up [¶]			X	X

* Follow-up visits are to be conducted on subjects who test positive to the Cardiac Amyloid Scintigraphy scan and/or are carrier of the V122I mutation. Window for the 6-month visit is ±2 weeks and for the 12-month visit is ±4 weeks.

† Height measured only at baseline visit. Subjects with weight >350 lb will not participate in the study.

‡ Includes BNP, NT-proBNP, galectin-3, troponin I and T.

§ Includes Vitamin A and RBP4 in on site spot urine.

¶ For participants with no TTR CA, a phone call follow-up will be conducted instead.

**In the event that PYP is unavailable due to supply shortage, the investigator has the option of using HDP until PYP becomes available again to ensure study continuation per FDA.

For every study visit, a checklist will be used to help ensure completion of all the study procedures. The checklist is also a guide that suggests the order in which the assessments should be performed (See [Appendix 3](#)).

TABLE OF CONTENTS

STUDY SYNOPSIS.....	2
LIST OF ABBREVIATIONS AND DEFINITIONS OF TERMS.....	9
1. INTRODUCTION	10
1.1 Background and Rationale	10
1.1.1 Transthyretin Biology	10
1.1.2 Transthyretin-mediated amyloidosis definition	10
1.1.3 Pathogenesis and Outcome.....	11
1.1.4 ATTR-CM and Heart Failure	11
1.2 ATTR-CM Population Burden.....	13
1.2.1 ATTR amyloid is an under-recognized cause of heart failure	13
1.2.2 Are Hispanics affected by TTR-CA?	14
1.2.3 TTR-CA from mutant protein has more severe phenotype than wild type	14
1.3 Natural History of Transthyretin Cardiac Amyloidosis	15
1.3.1 Clinical Characteristics and Outcome in ATTR-CA in TRACS	15
1.3.2 Predictors of Mortality	16
1.4 Therapeutic Options.....	17
1.4.1 Novel Therapies Require Early Identification of Affected Individuals	17
1.4.2 Tc-PYP & Tc-HMDP can detect TTR-CA without the need for an amyloid biopsy	
18	
1.4.3 Myocardial retention of Tc99-PYP is prognostic in TTR-CA	18

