2.1.1 Research Goal

The goal of our research is to change the approach to transthyretin cardiac amyloidosis, which is a devastating disease, by screening and early diagnosis, and by studying prospectively a cohort of older Blacks/Hispanics with heart failure in order to address the following aims and hypotheses:

Specific Aim 1: To determine the prevalence of ATTR CA in Caribbean Hispanics and Blacks with HF. The hypotheses to be tested include:

- (1) the prevalence of ATTR CA will be 10-15%
- (2) ATTRwt CA will be higher among Caribbean Hispanics compared to US Blacks, whereas the prevalence of ATTRm CA will be lower
- (3) the gender distribution of ATTR CA identified by this active ascertainment approach will be similar
- (4) disease progression will demonstrate that ATTRm is associated with a more rapid decline vs. ATTRwt
- (5) the accuracy of our clinic-based risk calculator will be confirmed in this large prospectively recruited cohort

Specific Aim 2: To demonstrate that circulating RBP4 concentration is integral to TTR tetramer stability which in turn determines the clinical characteristics of ATTR CA. We will measure TTR tetramer stability and RBP4 concentration in serum and urine collected in Aim 1. The hypotheses to be tested include:

- (1) TTR tetramer stability will be lower in ATTR CA and directly relate to RBP concentration
- (2) TTR tetramer stability will associate with clinical features and
- (3) Increased renal clearance of RBP4 in ATTR CA will be determined by measurement of RBP4 in plasma and urine.

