2.1.4 Selection Criteria

800 patients will be enrolled in this protocol. **Inclusion Criteria** will include: Black or Hispanic of Caribbean origin, Age \geq 60 years with heart failure and able to understand and sign the informed consent document after the nature of the study has been fully explained, prior to any study procedures. **Exclusion Criteria** will include confirmed primary amyloidosis (AL) or secondary amyloidosis (AA), prior liver or heart transplantation and active malignancy or non-amyloid disease with expected survival of less than 1 year, or heart failure attributable to ischemic or valvular heart disease.

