common. Among the 110 patients with hypertensive, non-amyloid HFpEF, or HCM, 93% had a grade 0 scan, and 6% had a grade 1 scan. In this application, while we anticipate subjects with grade 1 uptake of CARDIAC AMYLOID SCINTIGRAPHY will be low (<10%), we will explore the significance of a grade 1 scan result in the following ways. First, we will perform SPECT/CT imaging in some subjects with grade 1 myocardial retention of radiotracer to distinguish true myocardial uptake versus blood pool in the LV cavity. Those with the latter (grade 1 scans without myocardial retention of radiotracer but with blood pool in the LV cavity) will represent the false negative population, from which we can calculate the false negative rate. We can also determine if patients with grade 1 radiotracer uptake have a distinct clinical profile by biomarkers, echo, or functional measures and adverse outcomes as we are following patients prospectively in this study. The potential to have false positive with cardiac amyloid nuclear scintigraphy will be addressed by evaluation for AL cardiac amyloid in anyone who has myocardial retention of radiotracer greater or equal to grade 2, as this is the most common cause of a false positive scan. Every such case will be scrutinized and any subjects with normal TTR genotype but with testing or clinical features suggestive of CA will be referred for further characterization as part of routine clinical care for serum immunofixation electrophoresis and free-light chain assay to exclude light chain amyloidosis. While rare (incidence of 1:100,000), light-chain amyloidosis is the most common cause of a false positive scan. Other causes of a false positive nuclear scintigraphy that have been reported in the literature including hydroxychloroquine-mediated cardiotoxicity⁹⁸ and apolipoprotein A-1 amyloid cardiomyopathy⁹⁹ both of which are exceedingly rare and thus unlikely to be seen in our sample. *LVEF criterion:* ATTR CA is typically associated with HFpEF (LVEF>40%), but some patients with advanced disease can have moderate depressed systolic function. Notably, data is emerging that subjects with the Val122Ile variant more often present with a reduced EF. In order not to exclude this important cohort which is a focus of our efforts, we will enroll subjects with an EF >=30%. This may result in recruitment of controls with reduced EF, but we predict that exclusion of ischemic/valvular heart disease as the cause of HF will limit low EF control numbers. *Why is African ancestry not an inclusion criterion?* Given the association of the Val122Ile mutation with African ancestry, use as an inclusion criterion would enhance the identification of subjects. However, the strength of the association of Val122Ile with African ancestry is unknown. Additionally, requirement of African ancestry by genetic analysis would complicate enrollment. We will quantify ancestry¹⁰⁰ to determine its contribution to the observed phenotypes. *Will the Aim 2 on outcomes be confounded by participation in future clinical trials?* We will censor data on subjects enrolled in investigational trials in the longitudinal portion of the SCAN-MP study. If approved by FDA, we will not restrict access of eligible patients to any therapy that could be of clinical benefit. *Early vs. advanced disease:* We needed to choose between selecting a cohort with sufficient chance of identifying enough subjects with ATTR CA (those with HF) versus identification of subjects with early disease. Our active ascertainment of cases and use of Tc99-PYP or Tc99-HMDP, which identifies ATTR CA prior to echocardiographic changes^{101, 102} coupled with inclusion of subjects with mild forms of HF, should ensure identification of subjects with earlier disease than current practice. *Reduced RBP4 expression/Vitamin A confounding:* We are not able, in this design, to specifically determine the expression of RBP4 as this would require liver biopsy and quantitative PCR. However, data suggest that RBP concentrations vary not by expression but rather by clearance³⁸, as we have postulated. Furthermore, we are measuring

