8	Short physical performance battery			
9	Six-minute walk test			
10	QoL questionnaires			
11	Echocardiogram			

Form Completed by: _____

HEART FAILURE CLINICAL SCORE – NHANES CRITERIA

Clinical Variables	Check if present
Dyspnea/difficulty breathing	
Trouble with breathing (shortness of breath)	
Hurrying on the level or up slight hill	 1
At ordinary pace on the level?	 1
Do you stop for breath when walking at own pace?	 2
Do you stop for breath after 100 yards on the level?	 2
Physical examination	
Heart rate (beats/min)	
91 to 110	 1
111 +	 2
Rales/crackles	
Either lower lung field	 1
Either lower and either upper lung field	 2
Jugulovenous distension	
Alone	 1
Plus edema	 2
Plus hepatomegaly	 2
Chest X-ray film	
Cephalization of pulmonary vessels	
Interstitial edema	 1
Alveolar fluid plus pleural fluid	 2
Interstitial edema plus pleural fluid	 3
Alveolar fluid plus pleural fluid	 3

Score: ____

Form Completed by: _____

INCLUSION AND EXCLUSION CRITERIA

Inclusion Criteria	Yes	No
1. Black or Hispanic of Caribbean origin.		
2. Age \geq 60 years.		
3. Diagnosis of heart failure, confirmed by two methods:		
a. Modified criteria utilized by Rich et al. which include a history of acute pulmonary edema or the occurrence of at least two of the following that improved with diuretic therapy without another identifiable cause: dyspnea on exertion, paroxysmal nocturnal dyspnea, orthopnea, bilateral lower extremity edema or exertional fatigue, and		
b. NHANES CHF criteria with a score \geq 3.		
4. Left ventricular septal OR inferolateral wall thickness \geq 12 mm.		

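### Aim 1 is worded as ATTR-CA prevalence in Black and Caribbean Hispanic patients with HF, but the mandatory 12 mm wall criterion makes it a prevalence among HF patients whose walls are already thick

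*Combined protocol and SAP*

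**What the plan says.** - **Entry rule.** Inclusion criterion 4 in the Study Synopsis is "Left ventricular septal OR inferolateral wall thickness ≥ 12 mm". The list opens with "Every participant must meet all of the following inclusion criteria to be eligible for enrollment in this study". The eligibility form in Appendix 4 repeats the item.
- **Shorter list.** Section 2.1.4 gives race/ethnicity, then age and the rest as "60 years with heart failure and able to understand and sign the informed consent document". It mentions neither wall thickness nor ejection fraction (EF). Section 2.1.2 likewise describes only Black/Hispanic subjects over 60 with HF.
- **Target population.** Section 2.1.1 states Aim 1 as "To determine the prevalence of ATTR CA in Caribbean Hispanics and Blacks with HF". The synopsis words it as "To determine the prevalence of ATTR Val122Ile CA in Caribbean Hispanics and Blacks with HF". The two differ on whether the aim covers Val122Ile only, which is a separate matter; both end in HF without qualification. The synopsis design row and section 2.1.6 use the same population.
- **Denominator.** Section 2.1.6, Hypothesis 1, counts ATTRwt and ATTRm cases as a percentage of everyone enrolled and predicts 10-15%.
- **Early disease.** Section 2.2 relies in part on a tracer "which identifies ATTR CA prior to echocardiographic changes". It discusses the EF criterion and the absence of an ancestry criterion, but not the wall criterion.
- **Description of the cohort.** The end of section 1.3.2 calls the planned cohort unselected. Section 2.1.3 says that HF patients at increased risk of ATTR-CA are deliberately selected.

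**The concern.** Section 1.1.3 names heart wall thickening as a consequence of amyloid deposition. Requiring it for entry therefore selects on a feature of the disease whose frequency is being estimated. HF patients with both walls below 12 mm leave the denominator, and any cases among them leave the numerator. The remaining proportion equals prevalence in otherwise eligible HF patients only if nearly all of them meet the wall rule, or if ATTR-CA is as common below 12 mm as above it. The documents support neither condition.

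Two conclusions depend on this. One is the headline prevalence, which readers would apply to HF clinics generally. The other is the section 2.2 argument that the scan's ability to precede echocardiographic change helps to bring in early disease.

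**Working it through.** **Step 1. Who can be counted.** Section 2.1.5 has eligibility assessed at screening, and only those who qualify and consent go on to the visit with the scan. Criterion 4 is mandatory, so no patient with both walls below 12 mm is scanned under the plan. With total enrollment as denominator, numerator and denominator are both conditional on wall ≥12 mm.

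**Step 2. The plan's own figures.** N = 800 (section 2.1.7) and predicted prevalence is 10-15% (section 2.1.6).
- 800 × 0.10 = 80 cases; exact 95% interval 8.0-12.3%.
- 800 × 0.15 = 120 cases; exact 95% interval 12.6-17.7%.

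The lower end of the 80-160 cases in section 2.1.7 is reproduced. The upper end is not, since 160/800 is 20%. That mismatch is a separate point and plays no part here.

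**Step 3. From enrolled prevalence to HF prevalence.** Let
- p = prevalence at wall ≥12 mm (what the study estimates),
- q = share of otherwise eligible HF patients with wall ≥12 mm,
- r = prevalence below 12 mm divided by prevalence at or above it.

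Then P(HF) = q·p + (1 − q)·r·p, and the share of all cases not sampled is (1 − q)·r / [q + (1 − q)·r].

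The documents give neither q nor r. The values below are assumptions: q of 0.5 and 0.7, and r from 0 to 0.5. Taking r below 1 follows from wall thickening being an effect of the disease.

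Worked examples at p = 10%:
- q = 0.5, r = 0.25: 0.5 × 0.10 + 0.5 × 0.25 × 0.10 = 0.0625.
- q = 0.7, r = 0.5: 0.7 × 0.10 + 0.3 × 0.5 × 0.10 = 0.085.

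| q | r | P(HF) if p = 10% | P(HF) if p = 15% | Cases not sampled |
|---|---|---|---|---|
| 0.5 | 0 | 5.0% | 7.5% | 0% |
| 0.5 | 0.25 | 6.25% | 9.4% | 20% |
| 0.5 | 0.5 | 7.5% | 11.25% | 33% |
| 0.7 | 0 | 7.0% | 10.5% | 0% |
| 0.7 | 0.25 | 7.75% | 11.6% | 10% |
| 0.7 | 0.5 | 8.5% | 12.75% | 18% |

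**Step 4. Against the planned interval.** At p = 10%, five of the six values lie below 8.0%. At p = 15%, five of the six lie below 12.6%. The exact interval planned in section 2.1.8 measures sampling error within the enrolled population and cannot show this shift. The shift is zero if q = 1 or r = 1.

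**Step 5. Two effects in opposite directions.** For a fixed q, the more cases there are below 12 mm (larger r), the nearer the enrolled figure is to the HF figure. The largest distortion of the prevalence comes at r = 0, where no case is lost. Loss of cases and inflation of prevalence must not be added together.

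**The case against.** The selection is partly declared. Section 2.1.3 announces enrichment for risk, the denominator is openly total enrollment, and the EF, ischaemic and valvular criteria and the Table 3 quotas also separate the crude proportion from HF prevalence. Section 2.1.4 reads as an abridged paragraph, while the synopsis and the eligibility form agree. All of this stands. It makes criterion 4 one of several conditions and section 2.1.4 an incomplete list, not a rival rule. It does not correct the target population in Aim 1, because the enrichment statement never mentions wall thickness.

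A reader might go further and infer that the study cannot find early disease. The documents do not support that. A wall of 12 mm or more can have another cause; section 1.2.1 notes that these patients are often taken to have hypertensive heart disease. Uptake before any amyloid-related change could still be found in them. Section 2.1.6 analyses grade 1 scans as early disease, and the schedule footnote follows V122I carriers whatever the scan shows. Section 2.2 also concedes that an HF cohort was preferred to an early-disease one, and it claims only earlier disease than current practice.

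A reader might also apply a normal curve to the septal means and SDs in Table 1 and infer that about a quarter of cases fall below 12 mm. That ignores the inferolateral alternative. The table as it reads is also not dependable: LV mass of 304.6 g beside an index of 11.6 g/m² implies a body surface of about 26 m² (304.6/11.6).

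Lastly, a reader might infer that the HF figure is under a third of the enrolled one. That needs q near 0.3, for which the documents offer no source, together with r = 0.

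**Conclusion.** The point holds as a mismatch between the population sampled and the population named. Under the plan, Aim 1 estimates prevalence among patients who meet criterion 4 and the other entry rules. It is not a prevalence in Black and Caribbean Hispanic patients with HF, and the cohort is not unselected. ATTR-CA with both walls below 12 mm is not sampled. The pre-echocardiographic premise in section 2.2 therefore applies only to patients whose walls already reach 12 mm for any reason, though the relative claim of earlier disease than current practice may still be true.

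The direction, overstatement of HF prevalence, rests on ATTR-CA being less common below 12 mm than above it. The size cannot be determined from the documents. The 5.0-8.5% range for an enrolled 10% is illustrative and depends wholly on the assumed q and r. It shows that a shift larger than the planned confidence limits is possible, not that it will occur.

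**What to change.** Keep the entry rule and correct what is claimed.

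1. State Aim 1, Hypothesis 1, the synopsis design row and the reported estimate as prevalence in the population the criteria define: Black or Caribbean Hispanic, age ≥60, HF, LV wall ≥12 mm, EF >30% as in the synopsis and form, and HF not primarily ischaemic or due to severe valve disease. Remove the description of the cohort as unselected in section 1.3.2.
2. Reconcile section 2.1.4 with the full list in the synopsis and Appendix 4, for both wall thickness and EF. Section 2.2 writes the EF limit as 30% or more, so the passages need to be brought into line.
3. In section 2.2, limit the early-detection sentence to patients who meet the wall criterion, and state that disease with both walls below 12 mm is not sampled.
4. Record and report the number of otherwise eligible HF patients screened out for wall <12 mm, by ethnicity and sex. Present prevalence × q only as a sensitivity figure. It is a lower bound (the r = 0 case) only if patients passed over at chart review are logged; otherwise q is too high. This matters because the protocol echocardiogram is at Baseline, so wall data at screening apparently come from existing records.

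The cost is wording, some screening-log work (including confirming who was otherwise eligible), and a narrower headline claim. Sample size, procedures and planned tests are unchanged.
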